Treatments:

Patients will be administered a fixed dose of the following treatments:

- Galinpepimut-S: 4 WT1 derived synthetic analog peptides (galinpepimut-S) emulsified with the adjuvant Montanide for a total injection volume of 1 mL.
- Pembrolizumab: 200 mg

Patients will be administered subcutaneous (SC) sargramostim (from here on referred to as GM-CSF) at the site of the planned galinpepimut-S injection 2 days before (Day -2) and the day of (Day 1) each galinpepimut-S administration.

The overall treatment administration schedule is shown in the figure below:

Refer to [Section 5](#) for more details on treatment.

Dose-limiting Toxicities

All toxicities will be graded using NCI CTCAE Version 5.0 (published in November 2017), as per the following link:

https://ctep.cancer.gov/protocolDevelopment/electronic_applications/docs/CTCAE_v5_Quick_Reference_5x7.pdf.

The dose-limiting toxicity (DLT) window of observation will be:

For patients in the solid tumor arms: at least one (1) cycle following the co-administration of galipepimut-S in combination with pembrolizumab.

For patients in the AML arm: at least 8 weeks following the first administration of pembrolizumab

N.B.: this DLT assessment time window at the beginning of the study was chosen considering that (i). the treatment regimen in AML subjects includes the administration of HMA treatment (with cycle duration of at least 4 weeks), along with investigational therapy (pembrolizumab and galipepimut-S), and (ii). the timing of administration of the two sets of modalities is not linked, so that an adequate time interval to capture potential toxicities is secured.

A DLT is judged by the investigator to be possibly, probably, or definitely related to study drug administration.

For patients in the solid tumor arms:

Missing > 25% of the doses as a result of drug-related AE(s) during the period from first administration of galipepimut-S

and up until the completion of the first cycle of the co-administration of galinpepimut-S in combination with pembrolizumab, drug-related AE(s) which caused patient to discontinue treatment during Cycle 1, or Grade 5 toxicity, will be considered DLTs.

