- Second DLT (after reverting to the per protocol schedule) → skip the next GPS inoculation (scheduled for the next cycle, i.e., 3 wks ahead) and administer GPS 6 wks ahead (i.e., ‘spread out’) **twice thereafter**, i.e. **for 2 additional cycles** → DLT resolution → Return to per protocol schedule of GPS administration
- Third DLT (occurring either after reverting to the per protocol schedule or during the ‘spread out’ schedule to manage the 2nd DLT above) → Discontinue patient from study.

N.B.: In all above modifications of the dose density of galinpepimut-S, as all intervals (in weeks) between 2 successive GPS administrations are multiples of three (3) by design, following these rules, co-administration with pembrolizumab is always secured.

Stopping Rules:

- Development of any SAEs at least “possibly attributable” to the study agent(s) in 2 out of the first 6 patients in the study. In this case, the upper 90% one-sided CI bound for 2 patients with SAEs within 6 patients would be 66.7%, consistent with an excessive rate of toxicity.
- The fraction of patients experiencing an SAE at least “possibly attributable” to the study agent(s) exceeds 1/3, at any time during study implementation beyond the first 6 patients.
- Death at least “possibly attributable” to the study agent(s) within 30 days after the administration of the investigational treatment (GPS plus pembrolizumab).

If the study is stopped due to activation of the above rules, the safety data will be examined by the sponsor in consultation with investigators in order to determine how to proceed or whether to discontinue the study at large.

For patients in the AML arm:DLTs will be defined by toxicities observed in the first 8 weeks from study entry, as follows:

- a. Missing > 25% of the doses as a result of drug related AE during cycle 1 and/or 2

b. Drug-related AE which causes patient to discontinue treatment during cycle 1 and/or 2

- Grade 5 toxicity
- Grade 4 non-hematological toxicity (other than laboratory abnormality)
- Grade 3 non-hematological toxicity (other than laboratory abnormality; exception: fatigue, nausea, emesis, diarrhea, rash, infection, fever, or bleeding unless the event lasts more than 3 days despite optimal care)
- Grade 3 and 4 non-hematological lab abnormality, if any of the following occurs:
 - Medical intervention is required
 - Abnormality persists > 1 week
 - Abnormality results in drug-induced liver injury

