 - Any treatment-related toxicity that causes a greater than 3-week delay in initiation of cycle 2 and/or 3
 - Development of an immune-related AE resulting in withholding of pembrolizumab and initiation of steroids, for example, grade 2 or higher colitis/diarrhea, grade 2 or higher pneumonitis, grade 2 or higher transaminitis, any grade myocarditis (complete list currently shown in Table 5)

Any other toxicities in the AML arm will not be considered dose-limiting. Details for AML DLTs are provided in [Section 5.3.6.2](#).

Staggered Early Enrollment:

To minimize exposing subjects to the risk of potential unknown acute and subacute toxicities of combining HMA with the investigational therapy (pembrolizumab and galinpepimut-S) in the AML arm, the inter-dosing interval between the first two (2) subjects to be enrolled in this study arm will be 12 weeks.

DLT assessment and actions (unless stopping rules apply):

AML-specific DLTs will be considered separately from all other patients. Initially up to 6 patients will be enrolled in the AML cohort. If 2 or fewer patients of these first 6 patients have DLTs, enrollment can continue for up to another 6 patients in the AML arm with no dose adjustments made. If DLTs are observed in more than 2 patients of the first 6, the time interval between galinpepimut-S doses will be doubled for the inoculation following the one associated with the DLT, but pembrolizumab will continue as scheduled.

In the next 6 patients (patients 7 to 12), if again, 2 or fewer of these patients have DLTs observed, enrollment can continue. If DLTs are observed in more than 2 of patients 7 to 12, If DLTs are observed in more than 2 of patients 7 to 12, the time interval between galinpepimut-S doses will be doubled for the inoculation following the one associated with the DLT, but pembrolizumab will continue as scheduled.

If DLTs are observed in more than 2 patients of the first 6 (patients 1 to 6) and again in more than 2 patients of the next 6 (patients 7 to 12), the time interval between galinpepimut-S doses will be doubled for two (2) inoculations following the one associated with the DLT, but pembrolizumab will continue as scheduled. For example, if galinpepimut-S was given on a Q3W

schedule before the DLT occurred, it should be given Q6W for the 2 immediately subsequent administrations after the dosing event associated with the DLT, while keeping the pembrolizumab dose and frequency stable.

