5.3.6.2. AML-Specific Dose-Limiting Toxicities

For patients enrolled in the AML arm, the DLT window of observation will be defined by the first 8 weeks from study entry/administration of first galinpepimut-S inoculation.

The occurrence of any of the following toxicities during the first 8 weeks (from the time of administration of the first galinpepimut-S inoculation), if assessed by the investigator to be reasonably possibly related to study drug, will be considered a DLT:

1. Missing > 25% of the doses of investigational agent(s) as a result of drug-related AE during cycle 1 and/or 2
2. Drug-related AE which causes patient to discontinue treatment during cycle 1 and/or 2
3. Grade 5 toxicity
4. Grade 4 non-hematological toxicity (other than laboratory abnormality)
5. Grade 3 non-hematological toxicity (other than laboratory abnormality; exception: fatigue, nausea, emesis, diarrhea, rash, infection, fever, or bleeding unless the event lasts more than 3 days despite optimal care)
6. Grade 3 and 4 non-hematological lab abnormality, if any of the following occurs:
 - a. Medical intervention is required
 - b. Abnormality persists > 1 week
 - c. Abnormality results in drug-induced liver injury
7. Any treatment-related toxicity that causes a greater than 3-week delay in initiation of cycle 2 and/or 3 (the latter cycle being the first one whereby galinpepimut-S and pembrolizumab are co-administered).
8. Development of an immune-related AE (irAE) resulting in withholding of pembrolizumab and initiation of steroids, for example, grade 2 or higher colitis/diarrhea, grade 2 or higher pneumonitis, grade 2 or higher transaminitis, any grade myocarditis (complete list currently shown in Table 5)

Any other toxicities in the AML arm will not be considered dose-limiting.

Staggered Early Enrollment:

To minimize exposing subjects to the risk of potential unknown acute and subacute toxicities of combining HMA with the investigational therapy (pembrolizumab and galinpepimut-S) in the AML arm, the inter-dosing interval between the first two (2) subjects to be enrolled in this study arm will be 12 weeks.

AML-specific DLT assessment and actions will be as follows (unless stopping rules apply):

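### In the AML arm, the DLT items for missed doses, discontinuation and delay apply only before the first pembrolizumab dose, so non-immune haematologic toxicity that disrupts combination dosing is not counted

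*Combined protocol and SAP*

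**What the plan says.** Section 5.3.6.2 lists eight AML DLT items. Three concern dose disruption:

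- Item 1: "Missing > 25% of the doses of investigational agent(s) as a result of drug-related AE during cycle 1 and/or 2".
- Item 2: "Drug-related AE which causes patient to discontinue treatment during cycle 1 and/or 2".
- Item 7: a treatment-related toxicity causing a more than 3-week "delay in initiation of cycle 2 and/or 3 (the latter cycle being the first one whereby" the two agents are given together. The synopsis has the same item without the parenthesis: "Any treatment-related toxicity that causes a greater than 3-week delay in initiation of cycle 2 and/or 3".

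Items 4 to 6 are limited to non-haematologic events, item 8 to immune-related events that lead to withheld pembrolizumab and steroids, and item 3 is Grade 5. The list then closes: "Any other toxicities in the AML arm will not be considered dose-limiting".

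The window is stated in two ways. Section 5.3.6.2 has "The occurrence of any of the following toxicities during the first 8 weeks (from the time of administration of the first galinpepimut-S inoculation"), and the synopsis AML list agrees: "DLTs will be defined by toxicities observed in the first 8 weeks from study entry". The general DLT paragraph of the synopsis instead gives the AML window as "at least 8 weeks following the first administration of pembrolizumab".

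**The concern.** The more-than-2-of-6 rule is the AML arm's early check on adding galinpepimut-S and pembrolizumab to a hypomethylating agent (HMA). The dose-disruption items are the only ones through which a non-fatal, uncomplicated, non-immune haematologic toxicity can become a DLT. If they end before pembrolizumab begins, such toxicity counts while galinpepimut-S is given without pembrolizumab and stops counting once the combination under test starts.

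The two windows also leave sites unable to apply the rule uniformly. There is neither a safety monitoring committee (Section 6.5) nor an external data monitoring committee (Section 10.1), so these written rules carry more weight than usual.

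**Working it through.** **Inputs.** AML cycles are 3 weeks long and follow the investigational agents, not the HMA (Section 3.1.1). Galinpepimut-S is given without pembrolizumab at Weeks 0 and 3, and pembrolizumab is given every 3 weeks from Week 6 (Sections 3.1.1 and 5.2.4).

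**Calendar.** Cycle k starts at Week 3(k - 1). Cycle 3 starts at Week 3 x 2 = 6, the first pembrolizumab dose. This reproduces the protocol's own statement in item 7 that cycle 3 is the first co-administration.

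| Cycle | Due (Week) | Pembrolizumab | More than 3-week delay known after (due + 3) |
|---|---|---|---|
| 1 | 0 | no | - |
| 2 | 3 | no | 6 |
| 3 | 6 | yes, first dose | 9 |
| 4 | 9 | yes | 12 |
| 5 | 12 | yes | 15 |

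**Reach of the items.** Items 1 and 2 cover Weeks 0 to 6, when no pembrolizumab is due. Item 7 counts a late start of cycle 2 or 3, and toxicity that delays cycle 3 must arise before the first pembrolizumab dose. So 0 of the 3 items count disruption by toxicity arising on the combination.

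**Windows.**

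- Section 5.3.6.2, Weeks 0-8: one pembrolizumab dose (Week 6) and 8 - 6 = 2 combination weeks.
- Synopsis window statement, Weeks 6-14 at least: three doses (Weeks 6, 9 and 12) and 8 combination weeks.
- A more than 3-week delay of cycle 3 is known only after Week 9, so even that part of item 7 falls outside Weeks 0-8.

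**What is still caught.** Immune cytopenias with pembrolizumab withheld and steroids started (item 8, through the Table 5 row for other immune-related events); Grade 4 clinical events, and Grade 3 infection, fever or bleeding lasting more than 3 days (items 4 and 5); deaths (item 3); and related SAEs (stopping rules).

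**Size, on assumed rates.** Let p be the proportion of patients with an otherwise uncaptured disrupting event, X the number among 6, and suppose no other DLT occurs.

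- DLT rule: P(X >= 3) = 1 - sum over x = 0 to 2 of C(6,x) p^x (1-p)^(6-x).
- SAE rule: P(X >= 2) = 1 - (1-p)^6 - 6p(1-p)^5, with p replaced by p/2 if half the events are serious.

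At p = 0.30 the DLT rule gives 1 - (0.1176 + 0.3025 + 0.3241) = 0.256.

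| p | DLT rule trips if counted | SAE rule, all serious | SAE rule, half serious | SAE rule, none serious |
|---|---|---|---|---|
| 10% | 1.6% | 11% | 3% | 0% |
| 30% | 26% | 58% | 22% | 0% |
| 50% | 66% | 89% | 47% | 0% |

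With a captured DLT rate of 10% as well, and independence, the rule trips with 1.6% as written. Adding an uncaptured rate of 30% makes the combined rate 0.10 + 0.30 - 0.03 = 0.37 and the probability 39.4%.

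**The case against.** The strongest reply is that the gap is narrow and the existing protection is stronger than the rule at issue.

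- The missed event must be non-fatal, non-serious, non-immune, purely haematologic and uncomplicated, yet related to study drug and enough to disrupt dosing.
- Two related SAEs in the first 6 patients stop the study, and SAEs include important medical events, so many disrupting cytopenias could qualify.
- Tripping the DLT rule in the first 6 only doubles one galinpepimut-S interval. The DLT stop applies beyond 12 patients, which leaves 15 - 12 = 3 at the planned AML size.
- The AML experience described in Section 1.1.2, without pembrolizumab or HMA and so indirect, shows mostly transient count falls.

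All of this stands, and it limits the harm. It does not remove the defect.

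A second reply is that haematologic events were left out on purpose because HMAs cause cytopenias. That explains the absence of a haematologic-grade item. It does not explain why disruption from any related toxicity counts before Week 6 and not afterwards. Entry also requires adequate neutrophils and platelets (Table 1), and the solid-tumour list in Section 5.3.6.1 does tie missed doses and delay to combination therapy.

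A third reply is that cycles 1 and 2 were meant as combination cycles. Section 3.1.1 and the parenthesis in item 7 contradict that reading. If it was the intention, the text still needs correcting.

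**Conclusion.** The concern holds and should be fixed. On the protocol's own cycle definition, none of the three dose-disruption items reaches past the first pembrolizumab dose, and nothing else in the closed list picks up non-fatal, non-immune, uncomplicated haematologic toxicity. The window conflict is separate and plain: one pembrolizumab dose under Section 5.3.6.2 against three under the synopsis window statement.

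What is lost in real time is non-serious haematologic toxicity that stops or delays combination dosing. Such events are still reported as adverse events and discontinuations (Section 7.6.4.1), so the loss is in the early decision rule and not in the data. The calendar result rests only on the documents. The probabilities rest on assumed rates, because the documents give none.

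**What to change.** In Section 5.3.6.2 and the matching synopsis list:

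- Extend items 1 and 2 to cycles 3 and 4, keeping the present coverage of cycles 1 and 2.
- Extend item 7 to a late start of cycle 4. Add cycle 5 only if the window runs beyond 9 weeks after first pembrolizumab (Week 6 + 9 = 15).
- State one window: from first galinpepimut-S to at least 8 weeks after first pembrolizumab, that is Week 0 to at least Week 14. A late cycle 4, known after Week 12, then falls inside it.
- Make the later-DLT rule agree. Section 5.3.6.2 starts it after the first cycle of co-administration and the synopsis after the second. The second fits a DLT period covering cycles 3 and 4.

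No stand-alone haematologic-grade DLT is needed, given the HMA background.

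The cost is one wording amendment, with no extra visits or data. Each AML patient's DLT read-out moves from Week 8 to Week 14, 6 weeks later, which the synopsis window statement already implies. If the 12-week stagger runs from first dose to first dose, the second AML patient could start galinpepimut-S at the first patient's Week 12, but would not receive pembrolizumab until Week 12 + 6 = 18, after the Week 14 read-out.

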grade 3 or higher pneumonitis, grade 3 or higher nephritis, grade 3 or higher transaminitis, or any grade myocarditis in 2 out of the first 6 patients in the AML arm of the study. In this case, the upper 90% one-sided CI bound for 2 patients with SAEs within 6 patients would be 66.7%, consistent with an excessive rate of toxicity.

- The fraction of patients experiencing grade 3 or higher colitis/diarrhea, grade 3 or higher pneumonitis, grade 3 or higher nephritis, grade 3 or higher transaminitis, or any grade myocarditis exceeds 40%, at any time during study implementation beyond the first 6 patients in the AML arm.

If the study is stopped due to activation of the above rules, the safety data will be examined by the Sponsor in consultation with investigators in order to determine how to proceed or whether to discontinue the study at large.

Note: Dose modifications for HMA-related (known/expected) toxicities -for either azacitidine or decitabine- in AML patients will be based on the respective US Prescribing Information for these products. These documents are included as Appendices 12.1 and 12.2.

Procedures

After signing the informed consent, patients will enter the 28-day Screening period. At the baseline visit (Day -2), all pretreatment screening procedures/assessments must be completed, review of inclusion/exclusion criteria (including specific tumor histologic type verification, [e.g., TNBC]), and review of laboratory and tissue pathology results confirmed prior to enrollment and the first GM-CSF injection.

Patients will then enter the open-label treatment period which is approximately 111 weeks (777 days; 2.13 years) in duration; the last galinpepimut-S administration would occur at 84 weeks (day 588 days; 1.61 years).

Patients will be treated until progression, death, unacceptable toxicity (including activation of the stopping rules in either the solid tumor arms or the AML arm), or completion of 2 years of therapy with pembrolizumab, whichever occurs first.

A safety follow-up period will occur 30 days after the last administration of study drug. A follow-up phone call for serious adverse events will occur 90 days after the last dose of pembrolizumab or 30 days following cessation of study treatment if the patient begins new anticancer therapy, whichever is earlier. If the patient initiates new anticancer therapy, this must be reported by the investigator.

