- If no DLTs re-occur after the above periods of doubly 'spaced out' administrations, then the patient should revert back to the initial GPS Q3W schedule (as per the initial dosing frequency/ investigational agent administration schedule).
- If a DLT occurs after these dose modifications in subsequent cycles, the patient will be discontinued from the study.

The above dose density modifications in response to DLTs is further summarized in the bulleted list of actions below:

- First DLT → skip the next GPS inoculation (scheduled for the next cycle, i.e., 3 wks ahead) and administer GPS 6 wks ahead (i.e., 'spread out') **once thereafter**, i.e. **for 1 additional cycle** → DLT resolution → Return to per protocol schedule of GPS administration
- Second DLT (after reverting to the per protocol schedule) → skip the next GPS inoculation (scheduled for the next cycle, i.e., 3 wks ahead) and administer GPS 6 wks ahead (i.e., 'spread out') **twice thereafter**, i.e. **for 2 additional cycles** → DLT resolution → Return to per protocol schedule of GPS administration

- Third DLT (occurring either after reverting to the per protocol schedule or during the ‘spread out’ schedule to manage the 2nd DLT above) → Discontinue patient from study.
- N.B.: In all above modifications of the dose density of galipepimut-S, as all intervals (in weeks) between 2 successive GPS administrations are multiples of three (3) by design, following these rules, co-administration with pembrolizumab is always secured.

Stopping rules (for AML patients):

- Development of any SAEs at least “possibly attributable” to the study agent(s) in 2 out of the first 6 patients in the study. In this case, the upper 90% one-sided CI bound for 2 patients with SAEs within 6 patients would be 66.7%, consistent with an excessive rate of toxicity.
- The fraction of patients experiencing an SAE at least “possibly attributable” to the study agent(s) exceeds 1/3, at any time during study implementation beyond the first 6 patients.
- Death at least “possibly attributable” to the study agent(s) within 30 days after the administration of the investigational treatment (GPS plus pembrolizumab)

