- Development of grade 3 or higher colitis/diarrhea, grade 3 or higher pneumonitis, grade 3 or higher nephritis, grade 3 or higher transaminitis, or any grade myocarditis in 2 out of the first 6 patients in the AML arm of the study. In this case, the upper 90% one-sided CI bound for 2 patients with SAEs within 6 patients would be 66.7%, consistent with an excessive rate of toxicity.
- The fraction of patients experiencing grade 3 or higher colitis/diarrhea, grade 3 or higher pneumonitis, grade 3 or higher nephritis, grade 3 or higher transaminitis, or any grade myocarditis exceeds 40%, at any time during study implementation beyond the first 6 patients in the AML arm.

If the study is stopped due to activation of the above rules, the safety data will be examined by the sponsor in consultation with investigators in order to determine how to proceed or whether to discontinue the study at large.

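### The related-SAE stopping rules listed for AML patients are not worded for the AML arm, so if applied literally, non-fatal SAEs concentrated there may not trigger a formal stop

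*Combined protocol and SAP*

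**What the plan says.** Section 5.3.6.2 has a list of stopping rules headed as applying to AML patients. The Synopsis repeats it in its AML part.

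- **Early SAE rule.** Related SAEs "in 2 out of the first 6 patients in the study". The same words stand in the solid-tumor list (Section 5.3.6.1 and Synopsis).
- **Running SAE rule.** The share of patients with a related SAE "exceeds 1/3, at any time during study implementation beyond the first 6 patients". No arm is named.
- **Death rule.** A related death within 30 days of treatment stops the study.
- **Immune-toxicity rules.** Grade 3 or higher colitis/diarrhea, pneumonitis, nephritis or transaminitis, or myocarditis of any grade, "in 2 out of the first 6 patients in the AML arm of the study", or in a fraction that "exceeds 40%, at any time during study implementation beyond the first 6 patients in the AML arm".

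The Synopsis, under Procedures, describes the rules by arm: "activation of the stopping rules in either the solid tumor arms or the AML arm". Any of these stops leads to a review of the safety data by the sponsor with the investigators. Sections 6.5 and 10.1 give the safety monitoring committee and the external data monitoring committee as not applicable.

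**The concern.** Within one list, two rules are tied to the AML arm, one is tied to the study, and one is tied to nothing. A reader applying the text can fairly take the different words to mean different populations. The SAE rules also match the solid-tumor list word for word, as if carried over without adapting the denominator.

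The AML arm is the only one in which patients continue an HMA alongside galinpepimut-S and pembrolizumab. If its SAEs are counted against the whole study, up to 75 solid-tumor patients enter the denominator. What could be lost is the trigger that obliges a stop and a review, in a study without an independent committee. The population counted should not be settled only after events have occurred.

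**Working it through.** **Inputs.** Planned sizes are 15 AML patients of about 90 (Section 7.4). The thresholds are 2 of 6 and above 1/3 (Section 5.3.6.2). Random order of entry and all SAE rates are assumptions, because the documents give neither.

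**The plan's own figure.** The exact one-sided 90% upper bound for 2 events in 6 is the 0.90 quantile of Beta(3, 4) = 0.667. This matches the stated 66.7%. The number is right; the question is whom it counts.

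**2-of-6 rule, counted study-wide.** AML events alone can fire it only if at least two AML patients are among the first six.
- Hypergeometric (90 patients, 15 AML, 6 drawn): P(0) = 0.323 and P(1) = 0.416, so P(fewer than 2) = 0.739.
- If AML patients make up 10%, 20%, 30% or 50% of early entrants, the binomial P(fewer than 2 of 6) is 89%, 66%, 42% or 11%.
- The AML stagger pulls towards late AML entry: "the inter-dosing interval between the first two (2) subjects to be enrolled in this study arm will be 12 weeks". If five or more solid-tumor patients enter before the second AML patient, the first six hold at most one AML patient. The one-week stagger for the first three solid-tumor patients may slow those arms too.

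**1/3 rule, counted study-wide.**
- All 15 AML patients with events and none elsewhere: 15/90 = 17%.
- With 30 event-free solid-tumor patients enrolled, 15/45 equals 1/3 and does not exceed it. With 12, the same holds for 6/18.
- At 48 patients (8 AML, 40 solid-tumor) at least 17 events are needed, since 16/48 = 1/3. If all 8 AML patients have events, 9 of 40 solid-tumor patients (22.5%) must too. If 4 of 8 do, 13 of 40 (32.5%) must.

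**Both rules followed patient by patient.** Simulation with 100,000 runs per setting and random order: at least 2 events at patient 6, or a fraction above 1/3 at any later patient up to 90. Probability that either rule fires:

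| Solid-tumor related-SAE rate | True AML rate 50% | True AML rate 30% |
|---|---|---|
| 0% | 8% | 3% |
| 5% | 18% | 10% |
| 10% | 30% | 20% |
| 15% | 44% | 33% |
| 20% | 60% | 48% |
| 25% | 77% | 63% |
| 30% | just under 90% | just under 80% |
| Same rules counted in the AML arm only | 96% | 67% |

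At the higher solid-tumor rates the rule fires mostly on solid-tumor events, so it is not then a measure of AML safety.

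**What else covers the AML arm.**
- Related deaths and the named immune toxicities have their own rules.
- The AML DLT criteria in Section 5.3.6.2 cover further events, then close the list: "Any other toxicities in the AML arm will not be considered dose-limiting". Hematologic toxicity counts only through missed doses, discontinuation or delay.
- The DLT window is 8 weeks from the first galinpepimut-S dose in Section 5.3.6.2. In the Synopsis it is "at least 8 weeks following the first administration of pembrolizumab", which is about week 6 + 8 = 14.
- DLT-type events later in a patient lead to wider galinpepimut-S spacing and then to that patient's discontinuation.
- DLTs that stay above 2 per 6 beyond the first 12 AML patients do stop the study, but only three of the planned 15 remain by then.

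The residue is non-fatal related SAEs outside these. Examples are hematologic SAEs that do not delay, interrupt or end treatment, and SAEs other than the named immune toxicities after the DLT window.

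**The case against.** The strongest reply is that the rules are already arm-level in intent. The list heading, its place in the AML part of the Synopsis and the by-arm description under Procedures all say so. The Synopsis also considers AML DLTs separately from all other patients, and a study-wide rule would not need repeating in an AML list. The protocol uses these words loosely elsewhere: it calls the pooled solid-tumor cohorts a study arm. The 40% rule names the AML arm only for its starting point, not for its fraction. This stands as evidence of intent, and on that reading nothing is diluted.

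A reader might infer the stronger claim that the AML arm has no related-SAE stopping rule, or that AML events would go unseen. The documents support neither. The rules are listed for AML patients, SAEs must be reported within 24 hours (Section 6.4.1.3), and the sponsor may terminate the study at any time for clinical reasons (Section 10.4). Reporting and discretion do not oblige a stop, however.

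Two further points stand. The firing probabilities rest on solid-tumor rates that the documents do not supply, so no row of the table can be called the expected one. And HMAs themselves cause cytopenias and febrile neutropenia (Section 5.3.9), so AML-arm counting may trigger reviews of background events.

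**Conclusion.** The concern holds as a mismatch between wording and apparent intent that has a safety consequence. It does not show that a safeguard is missing. If the rules are read as AML-only, the remedy is a clarification.

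If they are applied as worded, AML-only events cannot fire the early rule in 74% of random entry orders. They cannot reach the 1/3 threshold at full enrollment, where 15/90 = 17%, without solid-tumor events. The 74% needs the random-order assumption; the 17% needs only that solid-tumor patients have no related SAEs. At a true AML rate of 50%, detection under study-wide counting runs from about 8% to just under 90% as the solid-tumor rate goes from 0 to 30%, against 96% with AML-arm counting. The other rules narrow the gap but do not close it. The wording should be corrected, since the remedy uses language already in the same list.

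**What to change.** - **AML list (Section 5.3.6.2 and Synopsis).** Give the early SAE rule the form already used for immune toxicities, "in 2 out of the first 6 patients in the AML arm of the study". In the 1/3 rule, define the fraction as that of AML-arm patients, beyond the first six patients in that arm.
- **40% immune-toxicity rule (same two places).** State that the fraction is of AML-arm patients.
- **Solid-tumor list (Section 5.3.6.1 and Synopsis).** Name the pooled solid-tumor arms as the population for both SAE rules.

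The thresholds and the 66.7% bound do not change.

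The cost is earlier reviews, some of them for SAEs that the HMA may explain. Counted in the AML arm through patient 15, the two SAE rules fire with probability about 12%, 25%, 39%, 53% and 67% at true related-SAE rates of 10%, 15%, 20%, 25% and 30%. Each leads to a sponsor and investigator review, not automatic termination. If the sponsor already meant AML-arm counting, the change adds no reviews beyond those intended.
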